9.1.3 Adverse Events of Medical Interest

Not applicable.

9.1.4 Serious Adverse Events

An SAE is an AE that meets one or more of the following outcome criteria:

- Results in death

Note: In the case of deaths, the event(s) leading to the death should be recorded and reported as SAE(s) with the outcome "Fatal". The death itself will not be reported as an event (SAE), unless the cause of the death is unknown (e.g., in case of unexplained or sudden death)

- Is life-threatening

Note: The term "life-threatening" in this definition refers to an event in which the patient is at immediate risk of death at the time of the event; it does not refer to an event which hypothetically might cause death if it was more severe

- Requires inpatient hospitalization or prolongation of existing hospitalization
- Results in persistent or significant disability/incapacity
- Is a congenital anomaly/birth defect
- Is medically important

Note: Medical and scientific judgment must be exercised in deciding whether an AE is believed to be "medically important". Medically important events may not be immediately life-threatening or result in death or hospitalization but may jeopardize the patient or may require intervention to prevent one of the other outcomes listed in the definition above

9.1.5 Events that Do Not Meet the Definition of Serious Adverse Events

PD will not be captured as an SAE unless the nature of the PD is different than expected (i.e., other diagnosis and/or signs/symptoms that are not typical of PD).

Note: PD may be reported as an SAE in the case of patient death, with death being the outcome of the event.

Elective surgery or other scheduled hospitalization periods that were planned before the patient was included in this trial are not to be recorded as SAEs, unless an outcome is considered serious.

Hospitalization for observation or convenience following the Sym015 infusions without an SAE occurring should not be recorded as an SAE, e.g., if a patient is hospitalized merely for

observation, or if a patient finalizes the infusion at a time of day requiring a convenience overnight stay in the hospital.

If procedures to support the treatment regimens require hospitalization, they should not be recorded as SAEs. However, in cases where a procedure results in complications requiring/prolonging hospitalization, this must be recorded and reported as an SAE.

9.2 Adverse Event Recording and Reporting Instructions

9.2.1 Adverse Event Recording Period

All AEs will be recorded from signing of informed consent for participation in the trial. The recording period ends at the time of the 1M FUP Visit.

Note: Patients who sign informed consent and are subsequently deemed to be screening failures will be followed for the occurrence of SAEs/AEs until it is determined that they will not be participating in the trial.

The Investigator must record all directly observed AEs and all AEs spontaneously reported by the patient. A general, open-ended type of question should be used to elicit a response from the patient, such as, “How have you been feeling?” or “Have you had any health problems since your last visit?”.

All AEs that occur in patients during the AE recording period must be recorded/entered on the AE section of the Case Report Form (CRF), whether or not the event is assessed as related to Sym015. If the AE is serious, the SAE report forms must also be completed and submitted. Refer to Section [9.3](#).

9.2.2 Diagnosis

A diagnosis should be recorded if possible. If no diagnosis is available, signs and symptoms should be recorded instead.

9.2.3 Severity

The Investigator will use the CTCAE v4.03 to describe the severity of an AE. If the severity of an AE is not specifically graded by the CTCAE guidance document, the Investigator should use the general definitions of Grades 1 to 5 as per the following, and use his/her best medical judgment to describe the severity of the AE:

- Grade 1: Mild
- Grade 2: Moderate

- Grade 3: Severe
- Grade 4: Life-threatening or disabling
- Grade 5: Death caused by the event

Changes in severity of AEs will be recorded.

Generally, an AE of CTCAE Grade 4 or 5 qualifies for SAE reporting to the Sponsor or designee. However, a laboratory abnormality of CTCAE Grade 4 does not need to be reported as an SAE, unless it meets one of the seriousness criteria in Section [9.1.4](#).

9.2.4 Relationship to Investigational Medicinal Product/Sym015

The Investigator must assess causal relationship to the IMP, Sym015. Relatedness has to be assessed and recorded within the initial report (CRF and SAE report form).

The causal relationship is an assessment of whether or not the event is related to the use of the IMP. It is not an evaluation of whether or not the event could hypothetically occur in the investigational patient population.

The causal relationship of an AE to the IMP, Sym015, will be rated as follows:

Not Related: The AE is not related to the IMP, which means the event:

- Does not follow a reasonable temporal sequence from drug administration
- Is readily explained by the patient's clinical state or by other modes of therapy administered to the patient
- The AE is clearly NOT related to the IMP

Unlikely Related: The AE is considered not related to the IMP based on the following:

- Does not follow a reasonable temporal sequence from administration of drug
- Could readily be a result of the patient's clinical state, environmental, or toxic factors, or other modes of therapy
- Does not follow a known response pattern to the suspected drug
- Does not reappear or worsen when the drug is re-administered

Possibly Related: The AE might not be related, but possibility cannot be ruled out with certainty and therefore would be considered related based on:

- Follows a reasonable temporal sequence from administration of drug

- Could readily have been a result of the patient's clinical state, environmental or toxic factors, or other modes of therapy
- Follows a known response pattern to the suspected drug

Probably Related: It has been determined with a high degree of certainty that the AE is associated with administration of IMP based on:

- Follows a reasonable, temporal sequence
- Cannot be reasonably explained by known characteristics of the patient's clinical state, environmental, or toxic factors, or other modes of administered therapy
- The AE disappears or decreases in severity upon cessation of drug, or reduction in dose.
- Follows a known response pattern to the suspected drug

Related: The AE is related to the IMP, which means the event:

- Follows a reasonable temporal sequence from drug administration
- Abates upon discontinuation of the IMP (de-challenge)
- Is confirmed by reappearance of the reaction on repeat exposure (re-challenge)
- Cannot be reasonably explained by the known characteristics of the patient's clinical state
- Is not likely to have been produced by the patient's clinical state or by other modes of therapy administered to the patient

9.2.5 Outcome

Outcome of the AE must be assessed by the Investigator utilizing one of the following terms:

- Recovered
- Recovered with sequelae (if recovered with sequelae, specify sequelae)
- Not recovered
- Fatal
- Unknown

Instructions for reporting changes in an ongoing AE during a patient's participation in the trial are provided in the instructions that accompany the AE CRF pages.

9.2.6 Follow-up of Adverse Events

All AEs should be followed until they are resolved or until the 1M FUP Visit, whichever comes first.

Note: Patients who sign informed consent and are subsequently deemed to be screening failures will be followed for the occurrence of SAEs/AEs until it is determined that they will not be participating in the trial.

9.3 Serious Adverse Event Recording and Reporting

All SAEs occurring at any time from signing of informed consent for participation in the trial and until the 1M FUP Visit must be recorded on the SAE Report Form and recorded as an SAE in the CRF.

Note: Patients who sign informed consent and are subsequently deemed to be screening failures will be followed for the occurrence of SAEs/AEs until it is determined that they will not be participating in the trial.

In case of an SAE, the Investigator must, within 24 hours of first awareness of the event, report the SAE to the Sponsor (or designee) by fax or e-mail. Fax number(s) and e-mail address(es) will be stated on the SAE Report Form and the SAE Report Form Completion Instructions. SAE follow-up information must also be reported to the Sponsor (or designee) within 24 hours of awareness.

SAEs still ongoing after the 1M FUP Visit should be followed on a regular basis according to the Investigator's clinical judgment, until the event resolves or until the Investigator assesses it as chronic or stable. The Sponsor (or designee) will pursue sufficient information and will return to the trial sites for such information as deemed required.

If the Investigator becomes aware of an SAE that occurred after the 1M FUP Visit and finds it to be related to the IMP (possibly-, probably-, or related to the IMP) or trial conduct, it must be recorded and reported to the Sponsor (or designee) as an SAE. These SAEs considered related to the IMP and occurring after the 1M FUP Visit will not be reported in the CRF but only on an SAE Report Form for recording in the Safety Database.

The Investigator should be aware of local reporting regulations to the Institutional Review Board (IRB)/Ethics Committee (EC). The Sponsor (or designee) will either supply the Investigator with the reports, which should be forwarded to the IRB/EC, or report directly to the IRB/EC depending on local regulations.

9.4 Safety Reporting to Health Authorities, Institutional Review Boards/Ethics Committees, and Investigators

Reportability of an SAE as a "suspected unexpected serious adverse reaction" (SUSAR) will be determined solely by the Sponsor, based on seriousness, causality and expectedness. In addition to SUSARs, the Sponsor or designee is responsible for reporting all relevant safety information regarding SUSARs, or other safety developments, to appropriate Health Authorities and central

IRBs/ECs, as well as participating Investigators. Requirements for reporting SUSARs to local IRBs/ECs will be handled via the Investigator. The timeline for notification of SUSARs is within 7 calendar days for fatal/life-threatening events and within 15 calendar days for all other SUSARs.

Additionally, the annual Development Safety Update Report (DSUR) will be submitted by the Sponsor or designee to all appropriate Health Authorities and central IRBs/ECs as per ICH Guidelines. Submission of the DSUR to local IRBs/ECs will be handled as per local regulations and/or requests.

9.5 Dose-Limiting Toxicities (Part 1 Only)

9.5.1 Definition of Dose-Limiting Toxicities

A DLT is defined as any of the following toxicities that occur during the DLT observation period, if considered related (causality rating of possibly, probably, or related) to Sym015:

1. Grade 3 non-hematologic toxicity regardless of duration, with the exceptions of:
 - a. Grade 3 nausea, vomiting, diarrhea, or fatigue lasting \leq 2 days with best supportive care
 - b. Grade 3 asymptomatic electrolyte abnormalities lasting \leq 3 days that are not considered clinically relevant by the Investigator and that resolve with medical therapy
2. Any Grade 4 non-hematologic toxicity, with the exception of:
 - a. Grade 4 asymptomatic electrolyte abnormalities lasting \leq 3 days that are not considered clinically relevant by the Investigator and that resolve with medical therapy.
3. Neutropenia that is:
 - a. Grade 3-4 febrile neutropenia
 - b. Grade 4 and sustained (i.e., ANC <500 per mm³, duration >5 days)
4. Thrombocytopenia that is:
 - a. Grade 3 with clinically significant hemorrhage
 - b. Grade 4 (platelets $<25,000$ per mm³)
5. AST/ALT elevation $>3\times$ ULN with bilirubin elevation $>2\times$ ULN that cannot be explained by factors not related to study drug
6. Inability to complete Cycle 1 at the assigned dose due to \geq Grade 3 toxicity

7. Treatment delays >2 weeks from the scheduled “next dose” due to \geq Grade 3 toxicity

9.5.2 Observation Period for Dose-Limiting Toxicities

The observation period for DLTs is defined as Cycle 1 with a final assessment 14 (± 2) days after the last dose of Cycle 1 or prior to dosing on C2/D1.

Cycle 1 must have been completed at the assigned dose of Sym015 for a patient to complete the DLT observation period.

9.5.3 Reporting of Dose-Limiting Toxicities

All presumed DLTs must be reported to the Sponsor or designee within 24 hours after the Investigator or designee have become aware of the event. In addition, DLTs fulfilling the SAE criteria must be reported in an expedited manner according to the procedure for SAEs, as outlined in Section [9.3](#).

9.6 Reporting of Infusion-Related Reactions

The definition of an IRR is included in Section [7.1.3.6](#).

All IRRs must be reported in the CRF as an AE with the term “Infusion-related Reaction” followed by a specification of symptoms (e.g., “Infusion-related Reaction with dyspnea and flushing”).

To facilitate ongoing safety review throughout the course of this trial, the occurrence of \geq Grade 2 IRRs must be reported to the Sponsor or designee within 24 hours of occurrence.

IRRs fulfilling the SAE criteria must be reported in an expedited manner according to the procedure for SAEs, as outlined in Section [9.3](#).

9.7 Pregnancy

If any trial patient becomes pregnant during the course of the trial, the patient must be discontinued from Sym015 immediately and the pregnancy must be reported to the Sponsor or designee according to the same timelines as an SAE. While pregnancy is not considered an AE, all pregnancies are tracked as SAEs within the safety database in order to follow-up on exposure to the fetus/infant.

Pregnancies reported in female partners of male trial patients must also be included in the database; therefore, a pregnant partner must provide informed consent before information can be collected.

All pregnancies must be followed up every third month to determine outcome (including premature termination) and status of mother and child. Pregnancy complications and elective terminations for medical reasons must be reported as AEs or SAEs as appropriate (trial patients only). Elective terminations for non-medical reasons should not be reported as AEs. Spontaneous abortion must be reported as an SAE.

Any SAE occurring in association with a pregnancy brought to the Investigator's attention after the patient has completed the trial and considered by the Investigator as possibly related to the IMP (possibly, probably, or related to Sym015), must be promptly reported to the Sponsor or designee.

All pregnancy information including follow-up information must be reported in a designated pregnancy form provided by the Sponsor or designee.

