5.3.5 End of Treatment and Follow-up Visits

An End of Treatment (EOT) Visit will be performed for all patients within 10 days following the decision to discontinue treatment.

The patient will return for a 1-Month Follow-up Visit (1M FUP) 30 (+7) days after the last dose of Sym015.

After the 1M FUP Visit, the Investigator will make every effort to obtain follow-up information on response assessment and/or overall survival (OS) about once every 2 months. Response assessment follow-up is required in the event of an ongoing stable disease (SD) or objective response (OR, defined as PR or complete response [CR]), as per the Response Evaluation Criteria in Solid Tumors (Version 1.1) (RECIST v1.1) ([29](#)) at the 1M FUP Visit, until PD or another therapeutic intervention is initiated. Survival follow-up is required until death, withdrawal of consent, trial site closure, or termination/end of the trial. Occurrence of one of these events constitutes the EOS for the patient. This continued follow-up does not require an in-person visit at the trial site, but may be obtained by collection of data/documentation.

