5.6 End of Trial

The end of trial will be reached at the latest 1 month (30 +7 days) after the last patient has been withdrawn from Sym015.

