Note: Peripheral blood for ctDNA analysis by Guardant 360 will be obtained for assessment of *MET*-amplification status. As data are acquired on concordance between findings in tumor tissue versus ctDNA, the Sponsor may decide to transition to screening for *MET*-amplification using Guardant360 analysis only (e.g., 2+ or 3+ amplification score) without requiring confirmation in a recent or newly performed tumor biopsy.

d. NSCLC *MET*^{Ex14Del} Cohort ONLY:

- Documented NSCLC meeting disease criteria as defined above
- Documented *MET*^{Ex14Del} (tumors need not be *MET*-amplified)

Note: *MET*^{Ex14Del} status to be documented according to local institutional standards. Assessment in ctDNA by Guardant360 technology or equivalent is allowed. Tissue from a recent* or newly performed pre-dosing tumor biopsy must be submitted for central assessment.

*Recent tumor biopsy, defined as one performed since last documented disease progression as part of the site's usual practice, and where no intervening antineoplastic therapy has been administered; otherwise tissue from a newly performed biopsy must be obtained and submitted.

- May have received prior therapy with *MET*-targeting and/or EGFR-targeting agents (antibodies or TKIs)
- Willingness to undergo a pre-dosing biopsy (mandatory unless a recent* tumor biopsy as defined above is available), and potentially a biopsy at the EOC2 (optional), from a primary or metastatic tumor site considered safely accessible for biopsy

Note: Peripheral blood for ctDNA analysis by Guardant 360 will be obtained for assessment of *MET*^{EX14Del} status.

8. If female and of childbearing potential, a negative pregnancy test
9. Male or female, either not of childbearing potential or agreeing to use a medically effective method of contraception as per institutional standards during the trial and for 4 months after the last dose of trial drug

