15. Known or suspected hypersensitivity to any of the excipients of the Sym015 drug product

16. Any other life-threatening illness, significant organ system dysfunction, or clinically significant laboratory abnormality, which in the opinion of the Investigator, would either compromise the patient's safety or interfere with the evaluation of the safety of the trial drug

17. Any kind of disorder that compromises the ability of the patient to give written informed consent and/or to comply with trial procedures or is unwilling or unable to comply with trial requirements at the discretion of the Investigator

18. Breast feeding, or plans by the patient (or the patient's partner) to become pregnant during treatment or within 4 months after the end of treatment

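### Section 9.7 makes a trial patient's pregnancy reportable only during the trial, so for women whose participation ends within 4 months of the last dose it falls short of the protocol's own post-dose window

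*Protocol*

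**What the plan says.** Three sets of statements in the Protocol bear on this point.

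- **Reporting trigger.** Section 9.7 opens with "If any trial patient becomes pregnant during the course of the trial, the patient must be discontinued from Sym015 immediately". The rest of that sentence requires the pregnancy to be reported on the SAE timeline. The section adds that pregnancies are kept in the safety database so that exposure of the fetus or infant can be followed. Once the patient has finished the trial, the remaining provision covers "Any SAE occurring in association with a pregnancy brought to the Investigator's attention after the patient has completed the trial", and only if the event is judged possibly, probably or definitely related to Sym015.
- **Post-dose window.** Inclusion criterion 9 (Section 6.1) requires effective contraception, where applicable, "during the trial and for 4 months after the last dose of trial drug". Exclusion criterion 18 (Section 6.2) bars plans by the patient or the patient's partner "to become pregnant during treatment or within 4 months after the end of treatment".
- **When the trial ends.** Section 5.6 states: "The end of trial will be reached at the latest 1 month (30 +7 days) after the last patient has been withdrawn from Sym015". For the individual patient, Section 5.3.5 states: "Survival follow-up is required until death, withdrawal of consent, trial site closure, or termination/end of the trial". Any of those events is the end of study for that patient.

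Partner pregnancies have their own clause in Section 9.7. It requires them to be entered in the database, subject to the partner's consent, and sets neither a time limit nor an SAE condition.

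**The concern.** Criterion 9 itself separates the trial from the 4 months after the last dose. The reporting trigger in Section 9.7 covers only the first of these. When a patient's participation ends before the 4 months are up, there is a stretch in which the protocol still wants pregnancy avoided but no longer asks to be told of one.

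Two things are at stake. Some pregnancies conceived within the window would have no outcome follow-up, which runs against the purpose Section 9.7 gives for tracking them. And the post-trial record would be selective: a pregnancy with a related serious event would be reported, while one that went normally would not. Section 10 plans no pregnancy-outcome analysis, so this concerns the safety database and not any planned estimate.

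**Working it through.** **Step 1: end of trial.** Section 5.6 gives 30 + 7 = 37 days after withdrawal of the last patient as the latest end, with 30 days as the nominal month.

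**Step 2: length of the window.** The Protocol says 4 months and does not define a month in days for this purpose. Taking 30 days per month gives 4 × 30 = 120 days; calendar months give 4 × 365.25/12 = 121.8 days.

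**Step 3: uncovered days for the last patients to stop.**

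Uncovered = window − (days from withdrawal to trial end) − (lag from last dose to withdrawal)

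The Protocol does not fix the lag. Two values are assumed: 0 days (withdrawal on the day of the last dose) and 16 days (the 14-day dosing interval plus the 2-day visit tolerance).

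| Window (days) | Trial end after withdrawal (days) | Lag 0 | Lag 16 |
|---|---|---|---|
| 120 | 30 | 90 (75%) | 74 (62%) |
| 120 | 37 | 83 (69%) | 67 (56%) |
| 121.8 | 30 | 91.8 (75%) | 75.8 (62%) |
| 121.8 | 37 | 84.8 (70%) | 68.8 (56%) |

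Counting a month as 28 days (112 days in all) gives 75 to 82 days with no lag and 59 to 66 days with the 16-day lag. For patients who leave through consent withdrawal or site closure, the gap depends on when that happens and is not computed here.

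**Step 4: does another provision close the gap?**

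- Section 9.2.1: "The recording period ends at the time of the 1M FUP Visit". Section 9.3 then takes later SAEs only if they are found related to Sym015 or to trial conduct.
- The post-trial sentence of Section 9.7 needs both an SAE and a judgement of relatedness, so an uncomplicated pregnancy does not qualify.
- Section 9.7 asks for all pregnancies to be followed every third month to outcome. That sets how often a pregnancy is followed; it does not extend the period in which a patient's pregnancy must be reported.
- The Planned Trial Period entry of the synopsis says, directly after defining the end of trial, that patients go on being followed for response and survival. Section 5.6 does not repeat this, and neither place mentions pregnancy.

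For example, a woman among the last to stop, withdrawn on the day of her last dose, who conceives on day 60 is inside the 4-month window and may be past the end of the trial. Nothing in the Protocol requires that pregnancy to be reported unless a related SAE follows.

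**The case against.** The strongest reply is that the gap is narrow. The trigger is the course of the trial, not the AE recording period, and Section 9.7 says that pregnancy is not an AE, so the end of AE recording at the 1-month visit does not limit it. A patient who stops well before the trial ends stays in survival follow-up, with contact about every 2 months, and months 2 to 4 after her last dose are still within the trial. This stands. A reader might infer that every patient's months 2 to 4 are uncovered; the text does not support that.

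A reader might also infer that partner pregnancies after the trial are excluded. They are not: the partner clause has no time limit and no SAE condition. It is only unclear on timing.

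Third, the 4 months are stated as a contraception and pregnancy-planning period, and a reporting period need not equal it. Little drug may remain by day 37. Table 1 gives preliminary first-dose half-lives of 158 h (6 mg/kg, N = 3) and 213 h (12 mg/kg, n = 1). Day 37 is 37 × 24 = 888 h, which is 888/158 = 5.6 or 888/213 = 4.2 half-lives. Under simple exponential decline, about 2% to 6% of the concentration would be left. So the protocol does not define these pregnancies as exposed, and that description would go too far. What remains is that the protocol chose 4 months as the period in which pregnancy should be avoided, and gives no reason for ending pregnancy reporting sooner.

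Finally, the 69% to 75% figures assume withdrawal on the day of the last dose. Section 5.6 counts from withdrawal, so any lag shortens the gap, as the table shows.

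**Conclusion.** The point holds in a limited form. It applies to female patients whose participation ends within 4 months of the last dose: those stopping near the end of the trial, or leaving through consent withdrawal or site closure. For them, an uncomplicated pregnancy conceived after participation ends is not reportable under the current text. Sponsor termination of the trial is a listed reason for stopping treatment in Section 6.3.1, so several patients could be in this position together.

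For the last patients to stop, about 83 to 92 of 120 to 122 days are uncovered with no lag, and about 67 to 76 days with the assumed 16-day lag. Most other patients are covered. Few pregnancies are expected in patients with advanced solid tumors, though the Protocol gives no figure. This is a cheap improvement to safety reporting; it does not touch an endpoint or an analysis.

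**What to change.** Reconcile Section 9.7 with Section 5.6, inclusion criterion 9 and exclusion criterion 18:

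- make a trial patient's pregnancy reportable if it occurs during the trial or within the 4-month post-dose window the protocol already uses, and follow it to outcome whether or not an SAE occurs;
- say that this duty continues after the end of the trial and after the patient's own participation ends;
- state the same period for pregnancies in partners of male patients;
- use one starting point for the window, since criterion 9 counts from the last dose and criterion 18 from the end of treatment.

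Adding a pregnancy question to the 2-monthly follow-up contact would not do the job. It reaches patients still in follow-up, who are already covered, and may never reach those whose trial has ended.

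The cost is a short change to Section 9.7 and slightly longer pregnancy reporting for a few patients. No visit, endpoint or treatment rule changes.
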